Anyone coming onto campus (students, employees or visitors) is required to follow the university COVID-19 safety guidelines that are posted on the campus website: https://campusready.ucdavis.edu/, which may include filling out the UC Davis Daily Symptom Survey during each visit and completing COVID-19 testing. Additionally, participants will be required to wear a mask during all study interactions, have their temperature monitored and maintain a 6-foot distance when possible (e.g., except Registered Nurses performing blood draws). For transport by study staff in UCD vehicles to study procedure sites, participants will be provided and required to wear a KN95 or N95 mask, face shield and to sit 6 feet away from the driver and any other passenger.

General study design: The study is designed as a parallel, 6-week study with a 2-week baseline period during which all subjects consume the provided low-sugar baseline diet and a 4-week intervention period during which the experimental beverages are consumed along with a low-sugar diet.

Baseline (Week 1-2): All subjects will consume a provided, standardized, low sugar, energy-balanced diet for approximately 9-13 days. All experimental procedures are conducted. **Intervention (Week 3-6):** Subjects will be stratified by gender and normal weight/overweight status and randomized to one of the two groups listed below:

- **1.** Sugar-sweetened beverages (SSB): 25% of estimated Ereq/day as sucrose in water (11% weight/w/w), flavored with unsweetened Kool-Aid and divided into 3 servings/day.
- **2. Orange Juice (OJ)**: 25% of estimated Ereq/day as the carbohydrate in OJ divided into 3 servings/day.

Subjects will consume three provided beverages/day along with provided, standardized, energy-balanced meals and snacks for approximately 28-33 days. All experimental procedures are repeated.

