Diets & weight monitoring: Approximately 2 weeks prior to the start of study, enrolled subjects will be scheduled at their convenience to report to Ragle HNRC. If Ragle HNRC is unavailable due to facility safety restrictions (due to the small dining and procedure rooms, the number of subjects that can be accommodated at this time is very limited) or schedules conflicts, the foyer at the entrance to Ragle HNRC will be used. Their height and body weight will be measured with a portable stadiometer and body weight scale. They will be provided with a body weight scale and asked to provide (via text or email) a daily, minimally clad, fasted body weight for the next 2 weeks and throughout the study. The purpose is to improve the accuracy of the initial estimation of Ereq and to facilitate the adjustment of energy intake required to maintain stable body weight. Also at this visit, female participants will be asked to take a urine pregnancy test.

Study diet is prepared by the study staff in the kitchen of the Ragle HNRC on the UC Davis campus. Subjects are restricted to eating only the study food provided during the entire study.

The effects of orange juice compared with sugar-sweetened beverage on risk factors and metabolic processes associated with the development of cardiovascular disease and type 2 diabetes

The initial daily Ereq of each subject will be calculated by the Mifflin equation with an adjustment of 1.5 for activity 108 . During the 2-week baseline period, all subjects consume an energy-balanced, low sugar diet that is 50% E_{req} carbohydrate, 35% fat and 15% protein. During the 4-week beverage intervention, the subjects receive diets that are matched as closely as possible to the baseline diet with the exception of the substitution of 25% E_{req} as the carbohydrate in sucrose-sweetened beverage or orange juice for 25% E_{req} complex carbohydrate. Subjects will return all uneaten food for calculation of daily intake. Diet energy will be adjusted as required to maintain stable body weight. If energy adjustment of the meals consistently fails to prevent weight gain or weight loss the subject will not be studied further.

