Beverage and meal pick-up/return: At appointments scheduled at their convenience, subjects will report to Ragle HNRC two times/week to pick up a 3- or 4-day supply of meals/snacks/beverages, and to return uneaten food and packaging. If Ragle HNRC is unavailable due to facility safety restrictions or schedules conflicts, the foyer at the entrance to Ragle HNRC will be used. Temperature will be measured using a contactless thermometer. Subject will be given a urine collection cup and and asked to provide a urine sample using the restroom in the foyer area. All exchanges of meal & beverage carrying cases and urine cup & urine sample will be conducted with both subject and study staff member wearing masks, face shields and maintaining a 6-foot distance at all time. Thus there will be a designated cart or area in the foyer upon which all carrying bag/supplies/samples will be set for dispensation or for turnin. The cart or area will also have a supply of sterile wipes and disposable gloves so all items can

The effects of orange juice compared with sugar-sweetened beverage on risk factors and metabolic processes associated with the development of cardiovascular disease and type 2 diabetes

be decontaminated prior to being picked up. Subjects who fail to pick up a new supply of meals/beverages (or make arrangements for it to be delivered to their homes) in time to allow for uninterrupted consumption as required by the protocol, will be dismissed from the study for non-compliance. Subject will need to fill out study diet report forms, physical activity questionnaires and food surveys. These forms will be made available to complete electronically and are used to assess diet palatability and quantity, activity level changes and to describe diet deviations. These reports will be reviewed by the Study Coordinator and communication through text, email or Zoom call will be used to discuss issues or request clarifications.

Compliance monitoring: The sweetened beverages will contain a biomarker (riboflavin). The biomarker will be assayed in urine collected 2 times/week during meal pick-up appointments. The subjects will be informed that they are being monitored for compliance, but not provided specifics as to the method. We have successfully used this method of enhancing compliance in three previous studies^{7, 14, 15}.

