To identify subjects who consume or consumed non-study foods that contained HFCS or cane sugar or consume alcoholic beverages during the study period, we will measure biomarkers for added sugar and alcohol intake. We will measure the delta ¹³C value of blood drops collected at baseline and at the end of 4 weeks of intervention. The Delta ¹³C content in the blood drop will be measured at the UCD Stable Isotope Facility. Delta ¹³C is a novel validated biomarker of added sugar intake because most plants have a low natural abundance of delta ¹³C, while that of corn and sugar cane is conspicuously higher ^{110, 111}. The foods with the highest amounts of delta ¹³C are pure corn products, and beverages, hard candies and desserts sweetened with HFCS or cane sugar. Sugar from sugar beets has a low natural abundance of delta ¹³C, therefore beet sugar will be used to sweeten the sucrose-sweetened beverages provided as part of the intervention. Delta ¹³C in blood is an indicator of added HFCS and sugar cane sucrose consumption over the prior 2 weeks ³. Because all the meals and snacks provided during the 6-week study have a very low HFCS and sugar cane content, and all subjects are consuming the same foods, all compliant subjects will exhibit low and comparable levels of blood delta ¹³C at both the end of the 2nd week and 6th week of study. Data from subjects with delta ¹³C blood values that are more than 2 standard deviations above the mean for all subjects will not be included in the statistical analyses.

To identify subjects who routinely consume alcohol we will assay urinary ethyl glucuronide (immunoassay, Thermo Scientific, Fremont, CA) in the urine samples collected at each meal pick-up visit. Detection of ethyl glucuronide in urine indicates recent alcohol consumption ¹¹² and is considered to be a specific, highly sensitive, and reliable marker of recent alcohol intake within the previous 5 days ⁴. Urinary ethyl glucuronide concentrations above the 500 ng/ml will be considered positive for alcohol intake. Urine will be monitored for alcohol intake upon collection, and subjects with positive values will be considered for dismissal. The subjects will be informed that they are being monitored for compliance to the requirement that they not consume non-study food, but will not be provided specifics as to the method.

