assumed that the subject is non-compliant with regards to consuming all or only the food provided, and the subject will not be further studied.

Subjects will also be withdrawn if there is failure to pick-up study beverages/meals or make other arrangements that will allow for uninterrupted consumption of study diet, failure to consume study meals or study beverages, or if there is evidence that non-study foods are being consumed.

12) Risks to Subjects

Pre-existing hyperlipidemia: During recruitment/screening, it may be determined that a potential subject qualifies for study, but has TG or LDL-C levels higher than the normal range (TG > 150 and < 400 mg/dl; LDL-C >130 and < 160mg/dl). Subjects identified with existing hypertriglyceridemia will be informed of the potential risk that consuming sugar-sweetened beverages during the study period will further increase their blood levels of TG or LDL-C. They will be informed they have the option to not participate in the study and advised to discuss their clinical report and the decision to participate in this study with their primary care physician.

Hyperlipidemia: Consuming sucrose-sweetened beverages for 4 weeks at 25% of energy requirements is likely to increase risk factors (TG, LDL-cholesterol, apolipoprotein B) for cardiovascular disease in hyperlipidemic and normolipidemic subjects. It is expected that any changes should be fully reversible when the subjects consume a healthy, low fructose diet. Therefore, at conclusion of study, the subjects will receive information about following a low saturated fat, low fructose diet. If analysis of fasting lipids at end of study indicates unfavorable changes to levels out of the normal range, the subject will be asked to return for a follow-up fasting blood draw. If lipids are still elevated, [name] will recommend further counseling with a Registered Dietitian and referral to primary care physician for treatment.

Diarrhea and gastrointestinal distress: Consuming 3 servings of sugar-sweetened beverage or orange juice/day can cause diarrhea, stomach aches, bloating, heartburn or acid reflux due to fructose malabsorption or the acid content of orange juice. It is also possible that the changes in the subject's normal dietary routine will cause gastrointestinal distress. Imodium is recommended to subjects who experience diarrhea. GasX or Pepto Bismol is recommended to subjects who experience gastrointestinal distress.

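### The delta 13C rule drops randomised subjects who have 4-week outcomes, using a cutoff relative to the sample, and no analysis restores them

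*Combined protocol and SAP*

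**What the plan says.** Section 7 (General study design) places randomisation at the start of the 4-week intervention, after the baseline diet: "Subjects will be stratified by gender and normal weight/overweight status and randomized to one of the two groups listed below".

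Several rules can then remove a subject, and none is limited to the baseline period:

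- **Weight drift** (section 7, Diets & weight monitoring): "If energy adjustment of the meals consistently fails to prevent weight gain or weight loss the subject will not be studied further". Section 11 repeats the rule and gives the presumption behind it: "assumed that the subject is non-compliant with regards to consuming all or only the food provided, and the subject will not be further studied".
- **Missed pick-up** (section 7, Beverage and meal pick-up/return): subjects who do not collect supplies "in time to allow for uninterrupted consumption as required by the protocol, will be dismissed from the study for non-compliance".
- **Intake** (section 11): withdrawal also follows "failure to consume study meals or study beverages, or if there is evidence that non-study foods are being consumed".
- **Alcohol** (section 7, Compliance monitoring): "Urine will be monitored for alcohol intake upon collection, and subjects with positive values will be considered for dismissal".

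The delta 13C rule in the same Compliance monitoring section is of another kind. Blood drops are taken at baseline and after 4 weeks of intervention, and subjects with "blood values that are more than 2 standard deviations above the mean for all subjects will not be included in the statistical analyses". It acts at analysis, on people who have finished.

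The data analysis plan in section 8 models the 4-week change from baseline in an ANCOVA on beverage, gender and protocol version, adjusted for BMI and the baseline outcome. It names no as-randomised population and no analysis that puts the delta 13C exclusions back.

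**The concern.** A week-4 delta 13C value is measured after randomisation. Excluding on it means that the groups compared are no longer exactly the groups randomised. The excluded subjects' lipid and uric acid outcomes are in hand, so leaving them out is a choice and not a missing-data problem.

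The cutoff adds a second difficulty. It is not an absolute level marking added-sugar intake. It is the mean plus 2 SD of the study's own subjects, so it tends to remove the upper tail whether or not anyone strayed from the diet. The number removed is therefore not a measure of non-compliance.

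With 24 per arm, one or two subjects matter. The plan has little slack: the pilot effect for apoB is 0.84 and the design detects 0.83. If a result depends on who was excluded, the reader should be able to see that, and the plan as written does not provide for it.

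**Working it through.** **Inputs from the documents.** 24 completers per group, 48 in all (section 4; section 8, Sample Size). Two-sided 0.05, 80% power, effect 0.83 SD; pilot effects 0.89 (LDL-C), 0.84 (apoB) and 1.02 (24-hour uric acid) (section 8). Cutoff at the all-subject mean plus 2 SD, sampled at two time points (section 7).

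**Assumptions.** All 48 comply, delta 13C values are normal, and excluded subjects are not replaced. The text does not say whether a high value at one time point is enough, so both readings are shown.

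**1. The plan's own figure.** Two-sample t-test, n = 24 per arm, noncentrality 0.83 × √(24/2) = 2.875 on 46 df: power 80.4%. The smallest effect detectable at 80% is 0.826. The stated 0.83 reproduces.

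**2. Expected removals when everyone complies.** P(Z > 2) = 0.02275. With a known mean and SD, the expected number is 48 × 0.02275 = 1.09, and the chance of at least one is 1 − (1 − 0.02275)^48 = 0.67. The rule uses the sample's own mean and SD, so the count was simulated:

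| Reading of the rule | Mean removed of 48 | P(at least one) |
|---|---|---|
| One time point (e.g. week 4) | 1.0 | 0.72 |
| Either time point, correlation 0 | 2.0 | 0.92 |
| Either time point, correlation 0.5 | 1.9 | 0.92 |
| Either time point, correlation 0.8 | 1.6 | 0.89 |

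Under the either-time-point reading the 95% range is 0 to 4. Exclusions triggered only by the baseline value rest on a measurement made before randomisation and cannot create arm-related selection. The figure relevant to selection is the week-4 one, about 1.0.

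**3. Power after removals, at 0.83 SD.**

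| Per arm | Removed in all | Noncentrality | Power |
|---|---|---|---|
| 24 | 0 | 2.875 | 80.4% |
| 23 | 2 | 2.815 | 78.6% |
| 22 | 4 | 2.753 | 76.7% |

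Two removals, evenly split, match the mean under the either-time-point reading at zero correlation. Four are the top of its 95% range.

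**4. Movement of the contrast.** Removing k of 24 subjects from one arm, with average residual d SD, shifts the arm mean by k × d / (24 − k):

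- k = 1, d = 1: 1/23 = 0.043 SD
- k = 1, d = 2: 2/23 = 0.087 SD
- k = 2, d = 1, same side: 2/22 = 0.091 SD
- k = 2, d = 2, same side: 4/22 = 0.182 SD

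For scale, the standard error of the contrast is √(2/24) = 0.289 SD, so one removed subject moves it by 0.15 to 0.30 of a standard error (0.043/0.289 and 0.087/0.289).

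**The case against.** The case for the rule as written is good. Specific Aims 1 and 2 ask about weight-independent effects under controlled feeding, and a complier analysis suits that question. The rule is pre-specified, objective and one cutoff for all. Section 8 has laboratory staff blinded to intervention. The sucrose drink uses beet sugar so that it does not raise the marker itself. Removals among true compliers should then be unrelated to arm. All of this stands, and it is why the planned analysis should remain primary. It does not cover a subject whose high week-4 value is real: that reflects eating behaviour after randomisation, and an objective assay does not make such behaviour independent of the assigned drink.

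A reader might go further and infer that the dismissals after randomisation bias the comparison. The documents do not support that. They expect 70% completion but do not say how much of the loss follows randomisation. The 2-week restricted diet, the first MRI and the first catheter day all come before the intervention and will account for some of it. Nothing in the text links dismissal to lipid response, in either arm. Selection from dismissals is a possibility of unknown size and direction.

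A reader might also look to the end-of-study safety draw in section 10 for outcomes on dismissed subjects. It is planned for the final week only, and its listed panel does not include apoB or uric acid. After a missed pick-up or a refused drink, full exposure may already have ended, and section 12 says of lipid changes: "It is expected that any changes should be fully reversible when the subjects consume a healthy, low fructose diet".

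**Conclusion.** The point holds for the delta 13C rule. It removes randomised subjects with 4-week outcomes by a sample-relative cutoff, and no analysis shows the result with them in. Under full compliance and normality, expect about 1.0 of 48 removed on the week-4 sample, or 1.6 to 2.0 if either time point counts. The cost is about 2 to 4 percentage points of power if one or two per arm are lost and not replaced, and a shift of 0.04 to 0.09 SD for one removed subject 1 to 2 SD from the arm mean. Neither figure shows bias, and the direction of any bias cannot be read from the documents. The sample-size calculation is not in error.

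**What to change.** Keep the planned complier ANCOVA as the primary analysis. In the data analysis plan, pre-specify beside it the same ANCOVA for all primary outcomes, including LDL-C, apoB and uric acid, in every randomised subject with 4-week data. Restore the delta 13C-excluded subjects to their randomised arm and show the two results together. As accompanying reporting, tabulate dismissals after randomisation and delta 13C exclusions by arm and reason.

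The cost is one rerun on data already collected, plus a table. The downside is that some restored subjects may have eaten added sugar, so the second analysis supports the first and does not replace it. It also cannot reach subjects dismissed before the second metabolic visit, who have no 4-week outcome. For them, the table is what lets a reader judge.

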Inclusion criteria: The first submission of this proposal to NIH limited inclusion to participants \leq 40 years of age with BMI \leq 28 kgm². The NIH reveiwers criticized this plan because it would preclude the ability to assess the effects of the 2 interventions across the metabolic spectrum of BMIs and detect differences in susceptibility between healthy and less healthy subjects. It was noted that inclusion in the statistical analysis of BMI and metabolic syndrome, liver fat and insulin sensitivity will allow us to gain insights on these variables in the response to both interventions. Therefore in the revised NIH application we expanded our inclusion criteria to include participants \leq 50 years of age with BMI \leq 35 kgm². In order to ensure that we will be able to enroll obese subjects, who are likely to have plasma concentration of glucose, triglyceride or LDL-C that are out of the normal ranges, we also revised our exclusion criteria for these parameters to the values shown below. We will study men and pre-menopausal women (age 18-50 y; BMI 20-35 kg/m² with body weight > than 50 kg) with self-reported stable body weight during the prior six months. We will study 24 subjects per group, requiring a total of 48 subjects

The effects of orange juice compared with sugar-sweetened beverage on risk factors and metabolic processes associated with the development of cardiovascular disease and type 2 diabetes

to complete research procedures. We anticipate a completion rate of 70% therefore expect to enroll a total of 72 subjects.

Exclusion criteria:

- Fasting glucose >125 mg/dl
- Evidence of liver disorder (AST or ALT >200% upper limit of normal range)
- Evidence of kidney disorder (>2.0 mg/dl creatinine)
- Evidence of thyroid disorder (out of normal range)
- Systolic blood pressure consistently over 140 mmHg or diastolic blood pressure over 90 mmHg
- Triglycerides > 400 mg/dl
- LDL-C > 160 mg/dl in combination with Chol:HDL > 4
- Hemoglobin < 10 g/dL
- Pregnant or lactating women
- Current, prior (within 12 months), or anticipated use of any hypolipidemic or antidiabetic agents.
- Use of thyroid, anti-hypertensive, anti-depressant, weight loss medications or any other medication which, in the opinion of the investigator, may confound study results
- Use of tobacco
- Use of marijuana
- Strenuous exerciser (>3.5 hours/week at a level more vigorous than walking)
- Surgery for weight loss

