Throughout the study more than 30 text messages and/or emails get exchanged between subjects and the study coordinators regarding schedules, body weight, diet issues such as hunger or food that needs to be replaced. Those subjects who are most able to clearly communicate any problems they are having regarding schedules, diet, beverages, are the subjects who are most likely to consider participation in our study to be a rewarding experience.

5) Study Timelines

Timeline: Our goal is to study 24 subjects (12/group) using the modified protocol and 24 subjects (12/group) using the original protocol. Ten subjects have already completed the original protocol. Based on an expected retention rate of 70%, we will enroll 35 subjects during Years 4-5 (spring 2021 to summer 2022) into the modified protocol. When we have achieved our sample size of 24 subjects completing the modified protocol, we will seek approval to resume conduct of the original protocol. If approval is not obtained due to the pandemic, we will enroll up to 24 more subjects into the modified protocol to achieve a final sample size of 48 (10 on original protocol, 38 on modified protocol).

Duration of individual subject's participation: ~6 weeks (40-47 days) **Duration of anticipated enrollment of all subjects:** April 1, 2018-August 30, 2023 **Estimated date of investigator completion of primary analyses:** January 31, 2024

6) Study Endpoints

Primary and secondary study endpoints: The primary endpoints are the changes in risk factors for metabolic disease which include blood lipid and lipoprotein levels. The secondary endpoints are hepatic lipid content, the fractional rate of *de novo* lipogenesis, and whole body insulin sensitivity.

The effects of orange juice compared with sugar-sweetened beverage on risk factors and metabolic processes associated with the development of cardiovascular disease and type 2 diabetes

Primary and secondary safety endpoints: The study intervention, which consists of 4-weeks consumption of 25%Ereq as orange juice or sucrose-sweetened beverages, is not associated with any short term safety risks.

7) Procedures Involved

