Experimental procedures: Procedures are performed as shown in the study schedule below (Table 2). This schedule is approximate and the 6-week length is approximate, as changes may

The effects of orange juice compared with sugar-sweetened beverage on risk factors and metabolic processes associated with the development of cardiovascular disease and type 2 diabetes

be made to accommodate subject availability and availability of the study facilities, equipment & personnel. Outpatient procedures will occur at the Ellison Building, University of California Davis Medical Center (UCDMC), and at Touro Metabolic Research Center (TMRC) in Vallejo, CA. Transportation from Davis to UCDMC and TMRC and will be offered by study using UCD Fleet Service vehicles. Subjects will be provided and required to wear a KN95 or N95 mask and face shield while in the vehicle and maintain a 6-foot distance from the driver and any other passenger. Participants who wish to provide their own transportation to the facilities will be reimbursed at the UCD mileage reimbursement rate. For subjects who provide their own transportation, a study staff commucation plan that will include a wake-up call if needed will be set up to ensure their arrival at TMRC or the Ellison Building on schedule.

The effects of orange juice compared with sugar-sweetened beverage on risk factors and metabolic processes associated with the development of cardiovascular disease and type 2 diabetes

Week	Procedure	Location	Time	Details	Compensation
Baseline ~ 2 weeks Energ			balanced baseline diet: carbohydrate (mainly starch50%Ereq), fat (35%Ereq) (15%Ereq)		
-2	Scale Pick-up	Ragle HNRC	TBD by subject	2 weeks prior to study start; at-home body weight scale pick-up visit	\$10
-2 - 6	Fasting BW	Home	pre-breakfast	Text, email or phone in fasting BW daily	\$65
0	Study Overview	Home	TBD by subject	Zoom meeting for study/schedule review & questions	\$10
0	1st Meal Pick-up	Ragle HNRC	TBD by subject	1st meal pick-up visit	\$10
1 - 2	Diet	Home/Ragle HNRC	TBD by subject	Daily consumption of provided baseline study meals Pick-up/dropoff for study meals; urine collection: 2 times/week	\$40
1	MRI#1	UCDMC Radiology	7:00	Hepatic & abdominal magnetic resonance imaging	\$50
1	Stool Collection #1	Home	TBD by subject	Stool collection	\$20
2	24-h UC #1	Home	TBD by subject	24 hour urine collection	\$30
2	Pre-TMRC Evening	Home	20:00, 23:00	Consumption of acetate tracer dose	\$40

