There are no direct benefits to the subjects for participating in the research.

14) Multi-Site Research: N/A

15) Community-Based Participatory Research: N/A

16) Sharing of Results with Subjects

The results that the will be shared with the subjects include the anthropometric results (body weight, waist and hip measurement) and the body composition results generated by DEXA. Upon completion of their participation in the study, subjects will be provided with copies of their clinical chemistry, lipid and blood reports, which were generated on the blood samples collected during screening and during the final week of study. Other study results will not be shared with subjects. In general they will not be available until the end of the 5-year study.

17) Prior Approvals

NIH, the funding agency, will be sent a copy of the IRB-approved Protocol and Consent form for this study, when it is available.

[name] will obtain approval to conduct this research from the Touro University, California Committee on Human Research.

The Human Radiation Use Research Application (Form 35) has approved conduct of the DEXA procedures.

The effects of orange juice compared with sugar-sweetened beverage on risk factors and metabolic processes associated with the development of cardiovascular disease and type 2 diabetes

The UC Davis BUA, #R2217B, for the laboratories of Drs. [name] and [name] was approved on 2/25/19 and is good through 2/28/22.

18) Provisions to Protect the Privacy Interests of Subjects

Following the 30-minute screening survey, most of the interactions with the potential and enrolled subjects that involve providing personal information are handled by the Study Coordinators, research and medical team. We anticipate that our experienced study coordinators and medical team will be able to make the subjects feel at ease with the research situation with honest, open answers about any concerns that the subjects may have. The only information we are unable to share with the subjects will be concerning the metabolic effects we anticipate that we will observe in subjects consuming sucrose. They will be able to share that the amount of sugar in the sugar-sweetened beverages represents an amount that is consumed daily by at least 13% of the US.

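### The pre-existing hyperlipidemia notice is defined for raised TG or LDL-C but, read literally, is given only to subjects with raised TG

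*Combined protocol and SAP*

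**What the plan says.** Section 12, under the heading Pre-existing hyperlipidemia, describes people who qualify at screening but have TG or LDL-C above normal. It gives TG above 150 and below 400 mg/dl, and "LDL-C >130 and < 160mg/dl". The next sentence assigns the action: "Subjects identified with existing hypertriglyceridemia will be informed of the potential risk that consuming sugar-sweetened beverages during the study period" may further increase TG or LDL-C. The sentence after that refers back to the same people. They are to be told that they need not take part, and advised to talk over their clinical report and their decision with a primary care physician.

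Section 4 sets the lipid limits for entry. TG above 400 mg/dl excludes a subject. For LDL-C the rule is compound: "LDL-C > 160 mg/dl in combination with Chol:HDL > 4". The inclusion text explains that the limits were widened so that obese subjects could be enrolled, "who are likely to have plasma concentration of glucose, triglyceride or LDL-C that are out of the normal ranges".

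The next paragraph of Section 12, Hyperlipidemia, says the sucrose beverage is likely to raise TG, LDL-C and apoB in people with or without raised lipids. It provides a repeat blood draw and referral if end-of-study lipids have worsened to abnormal levels.

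**The concern.** The paragraph describes one group and instructs staff about a smaller one. Subjects with raised LDL-C and normal TG are in the description but not in the instruction. Subjects with LDL-C of 160 mg/dl or more who are nevertheless eligible are outside even the stated range.

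This is an operative instruction about who is warned on the basis of their own screening result and reminded that they can decline. LDL-C is one of the lipids that the protocol expects the sucrose beverage to raise, and the entry limits were relaxed partly to admit people with abnormal values. A coordinator who followed the sentence to the letter would treat two groups with comparable anticipated risk differently. Nothing in the sample size, endpoints or analysis is at stake.

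**Working it through.** There is no stated figure to reproduce. The check sets the defining sentence, the action sentence (both Section 12) and the entry limits (Section 4) side by side.

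| Screening profile | Eligible on lipids? | In the stated range? | Named in the action sentence? |
|---|---|---|---|
| A. TG >150 and <400, LDL-C within entry limits | yes | yes | yes |
| B. TG not above 150, LDL-C >130 and <160 | yes | yes | **no** |
| C. TG not above 150, LDL-C exactly 160, or >160 with Chol:HDL of 4 or less | yes | **no** | **no** |
| D. TG not above 150, LDL-C >160 with Chol:HDL above 4 | no | – | – |

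**Profile B** is the main gap: described, eligible, and not assigned the notice.

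**Profile C** arises because the exclusion needs both conditions. The conditions for values above 160 do not contradict each other. Total cholesterol is at least LDL-C + HDL. A ratio of 4 or less means total cholesterol is at most 4 × HDL. Hence LDL-C + HDL ≤ 4 × HDL, so HDL ≥ LDL-C/3. With LDL-C above 160, HDL must exceed 160/3 = 53.3 mg/dl, and somewhat more once other cholesterol fractions are counted. The profile is narrow but possible. LDL-C of exactly 160 is not excluded at any ratio.

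**Does other text supply the notice before entry?**

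- Section 4, Screening for eligibility: consent is signed first and the fasting lipids are drawn afterwards. The consent discussion therefore cannot reflect the individual's screening result.
- Section 7, Table 2, week 0: the meeting is listed as "Zoom meeting for study/schedule review & questions", with no mention of screening results.
- Section 16: copies of the screening lipid report are given when participation is complete.
- Section 10 and the Hyperlipidemia paragraph of Section 12: review, repeat draw and referral, all at the end of study.
- Section 12, Blood collection: there is a result-based notice at screening, but for low hemoglobin or hematocrit, not for lipids.

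None of these gives profiles B or C a result-based lipid notice before entry.

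**The case against.** The strongest reply is that the slip corrects itself. The heading says hyperlipidemia, the preceding sentence says TG or LDL-C, and the warning itself is about a rise in TG or LDL-C. Staff would have to overlook all three to leave out a subject with raised LDL-C. That is fair, and it is why this is a minor point. It does not remove the mismatch in an instruction to staff, and it does less for profile C, which lies outside the printed range. The words about exceeding the normal range do describe values above 160, but the bracket beside them says otherwise.

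Three stronger readings are tempting, and the documents do not support them.

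- *LDL-C-only subjects are told nothing of the risk.* The consent form is not in the documents and may warn everyone about LDL-C. Section 12 acknowledges the risk for all subjects.
- *Staff are barred from filling the gap.* Section 18 says that what staff are "unable to share with the subjects will be concerning the metabolic effects we anticipate that we will observe in subjects consuming sucrose". But the same restriction, read that way, would also forbid the warning that Section 12 requires for raised TG. The same paragraph promises open answers to subjects' concerns, and Section 4 has the coordinator answer all questions. Section 18 should not be used as evidence here.
- *The number affected has a ceiling.* Section 5 says "Ten subjects have already completed the original protocol. Based on an expected retention rate of 70%, we will enroll 35 subjects" into the modified protocol, and that, if the earlier procedures cannot resume, "we will enroll up to 24 more subjects into the modified protocol". After the 10 completers and the 24 planned on the modified protocol, 48 − 10 − 24 = 14 completers remain. At 70% retention that is 14/0.70 = 20 enrolments, so 35 + 20 = 55, or 35 + 24 = 59 with the full allowance. Neither is a true upper bound: Section 4 expects 72 enrolled, and 72 − 10 = 62. Enrolment to date is not stated, and the notice goes to people who qualify at screening, some of whom may never enrol.

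**Conclusion.** The mismatch stands, as a minor wording point on subject protection. Read literally, eligible subjects with LDL-C above 130 mg/dl and TG not above 150 mg/dl miss three things before entry: the warning tied to their own result, the reminder that they may decline, and the advice to consult a physician. Among them, those with LDL-C of 160 mg/dl or more are also outside the stated range.

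How many people this concerns cannot be derived, because the documents give no distribution of screening lipids and no enrolment count to date. Confidence is high on the wording. Whether anyone would actually go without the notice is uncertain, since staff may well read the sentence as intended. The conclusion assumes that no result-based lipid notice exists in material outside the documents.

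**What to change.** Make two edits in the Pre-existing hyperlipidemia paragraph of Section 12:

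1. Let the action sentence begin: *Subjects with TG or LDL-C above the normal range*.
2. Give the LDL-C range as: *LDL-C > 130 mg/dl, including values of 160 or above admitted with Chol:HDL of 4 or less*.

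Profiles A, B and C are then all covered, and the paragraph agrees with its heading and with Section 4.

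The cost is a small protocol edit and the possibility that a few more qualifying people decline after the notice. Entry limits and the analysis are unchanged. Because the notice belongs to screening and Section 7 places randomization at the intervention step, it would reach both beverage groups alike.
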